8.1.3. Expectedness

An AE is considered "unexpected" if the AE is not listed in the Investigator Brochure or is not listed with the observed specificity or severity.

8.2. AE Reporting

All AEs must be collected and recorded in the subject's study records/source documents, in accordance with the Investigator's normal clinical practice, and on the CRF.

Each AE will be evaluated by the Investigator or designee for duration (onset/cessation), severity, causal relationship to the study drug, seriousness, action taken with the study drug, and resolution or outcome. Treatment given for an AE should be recorded as a concomitant medication with the AE as the indication for the treatment. Definitions for severity and causal relationship to the study drug are presented in [Section 8.2.1](#) and [Section 8.2.2](#), respectively. The definition for serious is provided in [Section 8.1.2](#).

8.2.1. AE Severity

The Investigator or designee will assess the severity of each AE according to the following definitions:

- Mild - Transient symptoms that do not influence performance of the subject's daily activities. Other treatment is not indicated.
- Moderate - Marked symptoms sufficient to make the subject uncomfortable. Moderate influence on performance of the subject's daily activities. Other treatment may be necessary.
- Severe - Symptoms cause considerable discomfort. Substantial influence on subject's daily activities. May be unable to continue the study, and other treatment may be necessary.

8.2.2. AE Relationship to Study Drug

The Investigator or designee will assess the relationship of each AE to study drug using his/her clinical judgment and according to the following definitions:

- Probably Related: An adverse event that is probably related to the use of the drug
- Possibly Related: An adverse event that might be due to the use of the drug. An alternative explanation (e.g., concomitant drug, concomitant disease) is inconclusive. The relationship in time is reasonable; therefore, the causal relationship cannot be excluded.
- Unlikely Related: An adverse event that might not be due to the use of the drug. An adverse event for which an alternative explanation (e.g., concomitant drug, concomitant disease) is more likely or the relationship in time suggests that a causal relationship is unlikely.
- Not Related: An adverse event that is not related to the use of the drug.

For the purposes of regulatory reporting, a causality of probably or possibly related will be mapped to related, while a causality of unlikely or not related will be mapped to unrelated.

8.3. SAE Reporting

The Investigator or designee will notify the appropriate Sponsor contact immediately after the SAE detection, observation, or report of occurrence (regardless of the relationship to study drug). The Sponsor contact information for SAE reporting is provided below:

Primary Contact

Chief Medical Officer: [name], PhD
Phone office: [contact]
Phone [contact]

Back-up Contact

Head of Development: [name]
Phone [contact]

SAE reports to be submitted to Contract Research Organization (CRO) ICON Safety Services

Email: [contact]

These SAE reports must contain the following information:

- Study name/number
- Study drug
- Investigator details (name, phone, fax, email)
- Subject number
- Subject initials
- Subject demographics

- Clinical event:
 - Description
 - Date of onset
 - Treatment (drug, dose, dosage form)
 - Adverse event relationship to study drug
 - Action taken regarding study drug in direct relationship to the AE If the AE was fatal or life-threatening
 - If applicable, cause of death (whether or not the death was related to study drug)
 - If applicable, autopsy findings (if available)

The person responsible for the study shall take care that the study has been carried out in accordance with pharmacovigilance regional/local regulations.

All SAE reporting will adhere to US Code of Federal Regulations (21 CFR Part 312.32) for IND drugs and 21 CFR 314.80 for marketed drugs (15-day alerts) or other regional/local regulations as applicable. The IRB(s)/IEC(s) will be notified of the alert reports per applicable regulations.

All AEs, including SAEs, will be followed to resolution when possible. All AEs and treatments administered for these AEs will be recorded on the CRF.

9. STATISTICS

9.1. Sample Size Determination

No formal sample size calculation is required. The approximate sample size (up to 40 healthy subjects in Part A, up to 40 healthy subjects in Parts B and C combined, up to 46 subjects with CG in Part D and Part D Extension combined if no subject participates in both, and up to 18 subjects with GALK-deficient Galactosemia in Part E) is not based on statistical considerations. The number of subjects is typical for Phase 1 studies of this type and is adequate to meet study objectives.

Note: The number of cohorts and/or total number of subjects may increase if the PK data reveal an insufficient exposure at 40 mg/kg (see [Section 1.4](#)). In Parts D and E, the overall number of subjects per cohort may be increased up to 8 subjects to address any potential lost-to-follow-up among subjects treated with either placebo or AT-007. In Parts D and E, subjects treated with study drug (placebo or AT-007) in a cohort may be randomized to treatment in another cohort (separate consent required) within the same Part (assuming subject had no safety or tolerability issues in the prior cohort) as long as there is a washout period ≥ 5 days between the last dose in a cohort and the first dose in the next cohort. Subject to certain timing considerations (see [Section 3.3.6](#)), Part D subjects may also participate in Part D Extension (separate consent required).

9.2. Statistical Methods

Detailed statistical methods will be provided in a Statistical Analysis Plan (SAP) that will be finalized before database lock.

NOTE: Part E and Part D Extension results might not be included in the CSR. If the Part E and/or Part D Extension results are not included in the CSR, they will be summarized and presented in a separate report or CSR addendum.

9.2.1. General Considerations

Safety measures including the baseline data will be summarized descriptively within each part (Parts A, B, C, D, E, and D Extension) of the study by each cohort (dose level of AT-007 and placebo), pooled AT-007 group, and pooled placebo group. Within each part of the study, PK data will be summarized by AT-007 dose group using descriptive statistics. In case of repeat cohorts, data from all cohorts of the same dose level will be combined for analysis.

For continuous outcomes, descriptive statistics will include the number of subjects, mean, 95% confidence interval (CI) for the mean, standard deviation (SD), median, minimum (Min), maximum (Max), 25th percentile, and 75th percentile. For categorical outcomes, the number and percentage of subjects will be presented. Descriptive statistics will generally be presented by AT-group. For summaries of continuous AT-007 PK concentration and parameter data, the coefficient of variation will also be presented.

For analyses of change from baseline, baseline will generally be defined as the predose assessment on Day 1 or Day -1, as scheduled. If this value is unavailable, the last nonmissing value prior to dosing will be used. Otherwise, missing observations will be treated as missing at

random, and no data imputation will be performed. All data from the CRFs, as well as any derived variables, will be presented in data listings.

SAS® version 9.4 or later will be used for all analyses.

9.2.2. Analysis Populations

Two analysis populations will be defined:

- Safety population: The safety population will consist of all subjects who are randomized and receive at least 1 dose of study drug. All analyses will be performed according to treatment received. This population will be used for all analyses of safety data.
- Pharmacokinetic (PK) population: The PK population will consist of all subjects who receive at least 1 dose of AT-007 and have sufficient concentration-time data to estimate at least one of the planned PK parameters, as determined by the study pharmacokineticist. This population will be used for all analyses of PK and biomarker data.

For Parts D and E, these populations may be defined separately for the SAD and MAD periods.

9.2.3. Subject Disposition

The number and percentage of subjects screened, screen failed, enrolled, randomized, dosed, and completing the study will be summarized. The number and percentage of subjects who prematurely discontinue the study will also be summarized along with reasons for discontinuation.

9.2.4. Drug Exposure and Compliance

A data listing, by subject, containing study drug dosing and dosing errors, if any, will be provided. Treatment compliance will be summarized using descriptive statistics.

9.2.5. Important Protocol Deviations

Important protocol deviations (IPDs) will be identified and documented based on a review of potential IPDs. The potential IPDs will be identified through programmatic checks of study data, as well as through review of selected data listings. The potential IPDs to be reviewed include, but are not limited to, subjects who:

- Did not meet inclusion/exclusion criteria
- Received disallowed concomitant medication
- Informed consent date obtained after date of first study procedure

Additional IPDs may be identified from clinical review of Investigator/designee comments or other data. Individual IPDs will be presented in a data listing.

9.2.6. Demographic and Baseline Characteristics

Demographic and baseline characteristics (including age, sex, race, ethnicity, weight, height, and body mass index) will be summarized using descriptive statistics. No formal statistical analyses will be performed.

The medical history of all subjects as well as the neurological history of subjects with CG and subjects with GALK-deficient Galactosemia will be coded by system organ class (SOC) and preferred term (PT) using the Medical Dictionary for Regulatory Activities (MedDRA) version 22.0 or higher. The number and percentage of subjects with abnormal findings in each SOC and each PT will be summarized.

9.2.7. Safety Analyses

The evaluation of safety will be based on the occurrence of treatment-emergent adverse events (TEAEs); discontinuations from study drug and/or the study because of AEs; clinical laboratory test results, physical examination findings, vital sign evaluations, and 12-lead ECGs results. All safety endpoints will be summarized descriptively. No statistical inference will be applied to the safety endpoints. Descriptive statistics will be calculated for quantitative safety data and frequency counts will be compiled for classification of qualitative safety data.

AEs will be coded by SOC and PT using MedDRA, version 22.0 or higher.

TEAEs are defined as AEs with onset on or after the date/time of the first dose of study drug.

Safety analyses will be described in detail in the SAP.

9.2.8. Pharmacokinetic (PK) Analyses

PK calculations will be performed using appropriate software, e.g., Phoenix™ WinNonlin® (Version 6.3 or higher, Pharsight Corporation) and/or SAS® (Version 9.4 or higher, SAS Institute Inc.).

PK parameters will be calculated using noncompartmental methods, using an appropriate model. Concentrations below the lower limit of quantitation (BLQ) will be treated as zero from the time of the first quantifiable concentration; embedded and terminal BLQ concentrations will be treated as “missing.” Actual sample times, if available, will be used in the PK analysis.

AT-007 concentration-time data and PK parameters will be summarized by study part and cohort (dose level) using descriptive statistics (n, mean, SD, median, minimum, maximum, percent coefficient of variation [CV%]).

Dose proportionality, the proportionality of a change in systemic exposure with a change in dose, may be assessed using a power model or other appropriate methods.

Details of the PK analyses, including any additional exploratory analyses, will be described in the SAP.

9.2.9. Biomarker Analyses

For Parts D, E, and D Extension, blood and urine levels of galactose, galactitol, and its other metabolites will be summarized using descriptive statistics. Details of these analyses will be provided in the SAP.

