2. OBJECTIVES AND ENDPOINTS

The primary objective of this multicenter, first-in-human study is the following:

- To evaluate the safety of single and multiple ascending doses of orally administered AT-007 in healthy adult subjects and adult subjects with CG or GALK-deficient Galactosemia

The secondary objectives of this study are the following:

- To evaluate the pharmacokinetic (PK) parameters of single and multiple doses of orally administered AT-007 in healthy adult subjects and adult subjects with CG or GALK-deficient Galactosemia
- To evaluate the effect of single and multiple doses of orally administered AT-007 on the level of galactitol, a biomarker of AR activity, in adult subjects with CG or GALK-deficient Galactosemia
- To evaluate the effect of single and multiple doses of orally administered AT-007 on the levels of galactose and its other metabolites in adult subjects with CG or GALK-deficient Galactosemia

The exploratory objectives are the following:

- To measure the levels of AT-007 in the cerebrospinal fluid (CSF) of healthy adult subjects

The primary endpoints of this study are overall safety and adverse events (AEs). Safety will be assessed by the following:

- AEs
- Clinical safety laboratory tests (hematology, chemistry, urinalysis)
- Physical examinations
- Vital signs
- Electrocardiograms (ECGs)

The secondary endpoints are the following:

- PK parameters ([Section 7.2](#)) in healthy subjects, subjects with CG, and subjects with GALK-deficient Galactosemia
- Galactose, galactitol, and other galactose metabolites in the blood of subjects with CG and subjects with GALK-deficient Galactosemia
- Urine galactitol for subjects with CG and subjects with GALK-deficient Galactosemia

The exploratory endpoints are the following:

- AT-007 level in the CSF of healthy subjects (Part C only)

PK samples will be stored for possible future analysis of AT-007 metabolites.

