Three dosing cohorts are planned for subjects with CG (Part D). The same subjects will receive both the single dose and the multiple doses. Within each cohort of 6 subjects, 4 subjects will be randomly assigned to AT-007 and 2 subjects will be randomly assigned to placebo. Following a single dose of study drug (AT-007 or placebo), there will be a 5-day washout. Subjects who tolerate the single-dose will receive 1 daily dose of the same study drug (AT-007 or placebo) for 27 consecutive days. The decision of whether each individual subject can start multiple dosing

will be made by the Investigator in consultation with the Sponsor. **No subject in Part D can start multiple dosing without explicit agreement from the Sponsor.** Subjects will complete the 27 days of treatment and the associated PK, PD, and safety assessments through the 2 days after the MAD portion and then have an EOS Visit at 28 days after the last dose.

The starting dose for Part D (i.e., for Cohort D1) was based on results from Part A (Cohorts A1 through A4) and Cohorts B1 and B2 and at 5 mg/kg was lower than the dose for Cohort B2 (10 mg/kg). The dose for Cohort D2 (20 mg/kg) was based on results from these cohorts plus Cohorts B3 and D1; results for Cohort C1 were also considered. The dose for Cohort D3 will be based on results from all cohorts in Parts A and B and Cohorts D1 and D2 and will not be higher than the dose for Cohort B4.

Before the study proceeds to Part E (SAD and MAD in subjects with GALK-deficient Galactosemia), safety data from all completed cohorts in Parts A, B, and D of the study will be evaluated by the SRC and all PK data from these cohorts will be evaluated by the Sponsor. The starting dose for Part E will not be higher than the highest acceptable dose in Part D at the time of starting Part E (after all subjects complete Cohorts D1 and D2 but may be before, during, or after Cohort D3). The dose for subsequent cohorts (if any) in Part E will be based on results from the previous cohort(s) in Part E.

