7 STATISTICAL METHODS

7.1 General

The statistical analysis will be conducted following the principles specified in the International Council for Harmonization (ICH), formerly the International Conference of Harmonization, Topic E9 Statistical Principles for Clinical Trials (CPMP/ICH/363/96).

All statistical tabulations and analyses will be done using SAS®, Version 9.4 or higher.

Unless otherwise noted, for continuous outcomes, descriptive statistics will include the number of subjects, mean, 95% confidence interval (CI) for the mean, standard deviation (SD), median, minimum (Min), maximum (Max), 25th percentile, and 75th percentile. For categorical outcomes, the number and percentage of subjects will be presented. Descriptive statistics will generally be presented by AT-007 group. For summaries of continuous AT-007 PK concentration and parameter data, the coefficient of variation will also be presented.

In the data listings, study day relative to first dose of study drug may be presented. Study day relative to first dose will be calculated as: event date - first dose date (+ 1 if event day \geq first dose date).

For analyses of change from baseline, baseline will generally be defined as the predose assessment on Day 1 or Day -1, as scheduled. If this value is unavailable, the last non-missing value prior to dosing will be used.

All data from the CRFs, as well as any derived variables, will be presented in data listings.

For safety summaries, the unscheduled and repeat assessments will not be summarized; however, all results will be included in the data listing.

Unless otherwise noted, the analyses will be done by Parts and actual treatment/dose received.

Three sets of outputs will be created: One set for Part A, B, C, and D, one set for Part D Extension and one set for Part E(as detailed below). In creating tables in 3 sets, parts already completed can be analyzed earlier than the whole study has been completed.

| Study Part | Study Population | Design | Table |
|---------------------|---|---|---|
| Study 1 art | Study 1 opulation | Design | 1 abic |
| Part A | Healthy Adult Subjects | SAD | Parts A, B, C, and D will be |
| Part B | Healthy Adult Subjects | MAD (QD for 7 days) | summarized under 1 st set |
| Part C | Healthy Adult Subjects | MAD (QD for 7 days) | |
| Part D | Adult Subjects with CG | SAD, 5-day washout, MAD (QD for 27 days) | |

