7.11 Analysis of Biomarker Data

For Part D and E:

- Plasma Galactitol, the analysis should evaluate maximum galactitol reduction (absolute change and percent change) defined as the lowest galactitol value on any of the following days of treatment (Day 1, Day 12, Day 32) vs. Galactitol level at baseline (calculated as a mean of 2 pre-dose measurements, such as Day -1 and Time-0 on Day 1 of dosing)
- Plasma Galactose, the analysis should evaluate the pre-dose galactose level on Day 12 and Day 32 vs. Galactose level at baseline (evaluated as a mean 2 pre-dose measurement, such as Day -1 and Time-0 on Day 1 of dosing)
- Whole blood Gal-1P the analysis should evaluate the pre-dose Gal-1P on Day 12 and Day 32 vs. Gal-1P level at baseline (evaluated as a mean 2 pre-dose measurement, such as Day -1 and Time-0 on Day 1 of dosing)

In addition, plasma galactitol changes will be analyzed based on below subgroup categories if data permit:

- Gender: Male / Female
- Age: $\langle 21 \text{ years } \rangle = 21 \text{ years and } \langle 30 \text{ years } \rangle = 30 \text{ years}$
- BMI: $<22 \text{ kg/m}^2 / 22-25 \text{ kg/m}^2 / >25 \text{ kg/m}^2$
- Enzyme activity: <0.1%, 0.1-0.4%, >0.4%

Urine galactitol levels will be provided as tabulated values and they will not be subjected to a formal analysis.

For genetic analysis, allele specific mutations will be reported as tabulated information

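### No AT-007 versus placebo estimate is planned for galactitol, and the lowest-value measure shows a fall even without a drug effect

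*Protocol*

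**What the plan says.** The objective in protocol section 2 is "To evaluate the effect of single and multiple doses of orally administered AT-007 on the level of galactitol". In each Part D cohort (protocol section 3.1), "4 subjects will be randomly assigned to AT-007 and 2 subjects will be randomly assigned to placebo". Part E has the same split, and the Extension is 3:1.

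For the analysis, protocol section 9.2.9 says that "blood and urine levels of galactose, galactitol, and its other metabolites will be summarized using descriptive statistics", and leaves the detail to the SAP. SAP section 7.11 is headed for Parts D and E and sets these measures:

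- Plasma galactitol: "maximum galactitol reduction (absolute change and percent change) defined as the lowest galactitol value on any of the following days of treatment" (Days 1, 12 and 32), set against "Galactitol level at baseline (calculated as a mean of 2 pre-dose measurements, such as Day -1 and Time-0 on Day 1 of dosing").
- For galactose in plasma, the SAP's instruction is that "the analysis should evaluate the pre-dose galactose level on Day 12 and Day 32 vs. Galactose level at baseline". Gal-1P follows the same pattern.
- Urine: "Urine galactitol levels will be provided as tabulated values and they will not be subjected to a formal analysis".

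On grouping, SAP section 7.1 says "Unless otherwise noted, the analyses will be done by Parts and actual treatment/dose received". The interval it lists for continuous outcomes is a 95% CI for a group mean.

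**The concern.** An objective about the effect of a drug, in parts with a randomised control, calls for a comparison with that control. The planned measures are changes from a subject's own baseline. Any shift shared by the arms stays in the AT-007 figure, whatever its source.

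One such shift is built into the galactitol measure: the minimum of many noisy values falls below a mean of two baseline values by construction. Galactitol results also inform the Part E starting dose (protocol section 1.4) and may end escalation in Part D (section 3.5). The Sponsor/CRO is unblinded in these parts (section 5.2), so a comparison left unspecified could be shaped after the data are seen.

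**Working it through.** The documents give no SD, effect size or power for any biomarker, so there is no stated figure to reproduce.

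**1. Is a contrast planned anywhere?**

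| Place | What it provides |
|---|---|
| Protocol 9.2.9 | Descriptive statistics |
| Protocol 9.2.2 | Biomarkers in the PK population (AT-007 recipients only) |
| SAP 7.5 | Biomarkers in the Safety population (placebo included) |
| SAP 7.11 | Change from own baseline, Parts D and E |
| SAP 7.4 | Subgroup forest plots of galactitol; plotted estimate undefined |
| SAP 7.10 | The SAP's only model: PK dose proportionality |
| SAP 8, tables | Galactitol, galactose and Gal-1P for Parts D and E, Safety population; none for the Extension |
| SAP 8, mean plots | The same markers for Parts D and E, PK population |

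None of these is an AT-007 versus placebo estimate. The table of populations also shows a conflict: a placebo column exists under SAP 7.5 but not under protocol 9.2.2 or in the SAP mean plots.

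**2. The lowest-value measure with no drug effect.** The sampling schedule gives 8 postdose samples on Day 1 and 9 samples (predose plus 8) on each of Days 12 and 32: 8 + 9 + 9 = 26. The expected minimum of 26 independent standard normal values is about -1.98. Dividing by a mean of two baseline values multiplies the expectation by about 1 + CV²/2. So:

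expected change ≈ (1 - 1.98 × CV)(1 + CV²/2) - 1

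At CV 10%: 0.802 × 1.005 - 1 = -19.4%. A simulation of 50,000 subjects per setting agrees:

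| Within-subject CV (assumed) | 26 independent samples | 26 samples, half the variance between days | 3 samples |
|---|---|---|---|
| 5% | -9.8% | -8.6% | -4.1% |
| 10% | -19.4% | -17.0% | -8.0% |
| 15% | -28.9% | -25.5% | -11.7% |
| 20% | -38.3% | -33.7% | -15.1% |

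The SAP does not say which samples enter the minimum. If it were one per day, the last column applies. Placebo subjects would show the same built-in fall.

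**3. Precision of an added contrast.** Assume log SD 0.35 and baseline correlation ρ of 0.5 to 0.7. The margin factor is exp(t × SE), with SE = 0.35 × √(1 - ρ²) × √(1/n₁ + 1/n₂).

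| Comparison | df | t | SE (ρ 0.7; 0.5) | 95% CI factor |
|---|---|---|---|---|
| One Part D dose, 4 v 6 pooled placebo | 18 - 4 - 1 = 13 | 2.160 | 0.161; 0.196 | ×/÷ 1.42; 1.53 |
| Extension, 21 v 7 (protocol) | 28 - 2 - 1 = 25 | 2.060 | 0.109; 0.132 | ×/÷ 1.25; 1.31 |
| Extension, 12 v 4 (SAP) | 16 - 2 - 1 = 13 | 2.160 | 0.144; 0.175 | ×/÷ 1.37; 1.46 |

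With log SD from 0.2 to 0.5 over the same ρ, the factors run 1.22 to 1.83, 1.14 to 1.48 and 1.20 to 1.72. All assume independent subjects, no dropout and, for the Extension, a single cohort.

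**4. When baseline adjustment helps.** Relative variance is 1 - ρ² for ANCOVA and 2(1 - ρ) for change scores: 0.51 against 0.60 at ρ 0.7. Chance baseline imbalance multiplies the ANCOVA variance on average by 1 + 1/(f - 2), where f is the within-group df before the covariate.

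- 4 v 6 (f = 14): 0.51 × 1.083 = 0.553, about 8% below 0.60.
- 4 v 2 (f = 4): 0.51 × 1.5 = 0.765, about 27% above 0.60.

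In a single 4:2 cohort the plain difference in log change is the better choice. Its SE is 0.35 × √0.60 × √(1/4 + 1/2) = 0.235 at ρ 0.7, or 0.303 at ρ 0.5. With df 4 (t = 2.776) the factor is ×/÷ 1.92 to 2.32.

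**The case against.** Safety is primary, the sample size is not statistically based, efficacy analyses are declared not applicable, and descriptive analysis is an open choice. That stands, and it rules out asking for a powered test. It does not stop the plan from giving an estimate with an interval for a stated objective.

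A reader might infer that drug and non-drug effects cannot be told apart in this trial. The documents do not support that. SAP section 7.5 keeps placebo subjects in the biomarker tables and section 7.1 groups by treatment received, so the arms can be read side by side, and a contrast needs no new data. The weakness is in the planned analysis.

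A reader might also infer that supervised meals, fasting or clinic stay do move galactitol here. The documents do not show it. Subjects follow the restricted diet for at least 3 months before screening and keep their usual diet (protocol sections 4.2.1 and 5.5). Day -1, Day 12 and Day 32 are all fasted arrivals, and the Day 32 predose sample is taken on arrival from home. The lowest-value rule needs no such assumption.

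Finally, pooled placebo is imperfect. Cohorts are sequential, so with full enrolment four of the six Part D placebo subjects are non-concurrent with a given dose. Subjects may also enter more than one cohort (protocol section 4.4). Both points stand and are carried into the fix.

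**Conclusion.** The point holds as a gap in the planned analysis. No biomarker estimate uses the randomised control, and the galactitol measure carries a built-in fall of about 10% to 38% with 26 independent samples at a CV of 5% to 20%. The CV is an assumption, and the fall is smaller if few samples enter the minimum. The population conflict and the missing main analysis for the Extension are plain on the page and need no assumption.

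An added contrast would be imprecise but usable against pooled placebo and in the Extension. Within a lone 4:2 cohort, which may be all of Part E, it would say little. This is a cheap improvement and does not threaten the primary safety objective.

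**What to change.** In SAP section 7.11:

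- For log plasma galactitol (secondary), report the baseline-adjusted ratio of each AT-007 dose to placebo pooled within Part, with a 95% CI. Use fixed predose times: Day 32 in Parts D and E, Day 90 in the Extension. Label it estimation only, with no test.
- Do the same as exploratory analyses for galactose (Parts D, E and Extension) and Gal-1P (Part D and Extension only). SAP section 4 already makes galactose exploratory, and protocol section 1.1.3 says that Gal-1P does not form in GALK deficiency.
- Include a subject term where subjects enter more than one cohort, and state that pooled placebo is partly non-concurrent.
- For a single 4:2 cohort, report the unadjusted difference in log change instead of ANCOVA.
- Keep the lowest-value measure as descriptive, shown for both arms.

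Use the Safety population, placebo included, for every biomarker table and plot, and align protocol section 9.2.2 with it. The cost is one extra table per Part, no new data, and wide intervals shown as such.
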